16. Abnormal laboratory results at screening: Liver tests: either aspartate aminotransferase (AST), alanine aminotransferase (ALT), or alkaline phosphatase (ALP) > 2.0 × upper limit of normal (ULN) or total bilirubin > 1.5 × ULN (except for subjects with Gilbert Syndrome).
17. White blood cell count < 3,000 cells/mm³ (< 3 × 10⁹/L in SI [international system] units).
18. Hemoglobin < 10 g/dL.
19. Subject is currently enrolled in another investigational study unless a washout period, as described in table 5-1, will be performed.
20. Donation or transfusion of blood, plasma, or platelets within 90 days prior to inclusion.
21. Pregnant or nursing (lactating) women, where pregnancy is defined as the state of female after conception until the termination of gestation, confirmed by a positive HCG laboratory test (> 10 mIU/mL).

22. Women of childbearing potential, defined as all women physiologically capable of becoming pregnant, must use effective contraception during the study and for 16 weeks after stopping treatment. Highly effective contraception methods include:

- Total abstinence (when this is in line with the preferred and usual lifestyle of the subject. Periodic abstinence (e.g., calendar, ovulation, symptothermal, post-ovulation methods) and withdrawal are not acceptable methods of contraception.
- Female sterilization (have had surgical bilateral oophorectomy with or without hysterectomy) or tubal ligation at least six weeks before taking study treatment. In case of oophorectomy alone, only when the reproductive status of the woman has been confirmed by follow up hormone level assessment.
- Male sterilization (at least 6 months prior to screening). For female subjects on the study, the vasectomized male partner should be the sole partner for that subject.
- Combination of any two of the following (a+b or a+c, or b+c):
 - a. Use of oral, injected or implanted hormonal methods of contraception or other forms of hormonal contraception that have comparable efficacy (failure rate <1%), for example hormone vaginal ring or transdermal hormone contraception.
 - b. Placement of an intrauterine device (IUD) or intrauterine system (IUS).
 - c. Barrier methods of contraception: condom or occlusive cap (diaphragm or cervical/vault caps) with spermicidal foam/gel/film/cream/vaginal suppository.

In case of oral contraception, women should have been stable on the same pill for a minimum of 3 months before taking study treatment.

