7.3 Liver safety monitoring

To ensure patient safety and enhance reliability in determining the hepatotoxic potential of an investigational drug, a standardized process for identification, monitoring and evaluation of liver events has to be followed.

Liver events are divided into two categories:

- Liver events of special interest, which consist of liver function test (LFT) elevations.
- Medically significant liver events that are considered as serious adverse events and consist of marked elevations of LFTs and / or pre-specified adverse events.

Please refer to [Table 14-1](#) in [Appendix 2](#) for complete definitions of liver events.

Any liver event that meets the criteria for “**medically significant**” event, as outlined in [Table 14-1](#) of [Appendix 2](#), should follow the **standard procedures for SAE reporting** as described in [Section 7.2](#).

Every liver event as defined in [Table 14-1](#) of [Appendix 2](#) should be followed up by the investigator or designated personal at the trial site as summarized below.

- Repeat the LFT to confirm elevation as appropriate.
- Discontinue the investigational drug if appropriate.
- Hospitalize the patient if appropriate.
- Assess the causality of the liver event via exclusion of alternative causes (e.g., disease, co-mediations).
- An investigation of the liver event needs to be followed until resolution.

These investigations can include serology tests, imaging and pathology assessments, hepatology consultancy, based on the investigator's discretion. All follow-up information and the procedures performed should be recorded on appropriate CRF pages, including the liver event overview CRF pages.

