Normal blood pressure will be defined as a systolic pressure of 90 to <120 mmHg, and a diastolic blood pressure of 60 to <80 mmHg. Notable blood pressure will be hypertension (systolic blood pressure of ≥ 140 mmHg and/or diastolic blood pressure of ≥ 90 mmHg) or hypotension (systolic blood pressure of <90 mmHg and/or a diastolic blood pressure of <60 mmHg). A blood pressure indicative of prehypertension (systolic blood pressure of 120 to

<140 mmHg and/or diastolic blood pressure of 80 to <90 mmHg) will not be regarded as notable.

A normal pulse rate will be defined as a rate of 60 to 100 beats per minute (bpm). Notable pulse rates are a rate below 60 bpm (bradycardia) or above 100 bpm (tachycardia). Whether action needs to be taken to address notable vital signs will be decided by the investigator, taking into account the overall status of the patient. No specific action is foreseen as part of the study protocol.

14 Appendix 2: Liver event definitions and follow-up requirements

Table 14-1: Liver Event Definitions

	Definition/ threshold
Adverse event of special interest	
Laboratory values	ALT or AST > 3 x ULN ALP > 2 x ULN TBL > 1.5 x ULN
Medically significant event (SAE)	
Laboratory values	ALT or AST > 5 x ULN (with or without TBL > 2 x ULN [mainly conjugated fraction]) ALP > 5 x ULN (with or without TBL > 2 x ULN [mainly conjugated fraction]) TBL > 3 x ULN Potential Hy's Law cases (defined as ALT/AST > 3 x ULN and TBL > 2 x ULN [mainly conjugated fraction] without notable increase in ALP to > 2 x ULN)
Adverse events	Any clinical event of jaundice (or equivalent term) ALT or AST > 3 x ULN accompanied by general malaise, fatigue, abdominal pain, nausea, or vomiting, or rash with eosinophilia Any event that links to a preferred term (PT) in the MedDRA dictionary falling under the SMQ sub-module "Drug-related hepatic disorders – severe events only"* or any "Hy's law case" PT

* These events cover the following: hepatic failure, fibrosis and cirrhosis, and other liver damage-related conditions; non-infectious hepatitis; benign, malignant and unspecified liver neoplasms

Table 14-2: Liver Event Follow Up Requirements

Criteria	Event type	Actions required	Follow-up monitoring
Potential Hy's Law case ^a	Medically significant	Discontinue the study drug immediately Hospitalize, if clinically appropriate Report to Novartis as an SAE Establish causality	ALT, AST, TBL, Alb, PT, ALP and γ GT until resolution ^c (frequency at investigator discretion)

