ALT or AST			
> 8 x ULN	Medically significant	Repeat LFT within 48 hours If elevation persists, discontinue the study drug immediately Hospitalize if clinically appropriate Report to Novartis as an SAE Establish causality	ALT, AST, TBL, Alb, PT, ALP and γ GT until resolution ^c (frequency at investigator discretion)
> 5 to \leq 8 x ULN	Medically significant	Repeat LFT within 48 hours If elevation persists for more than 2 weeks , discontinue the study drug Report to Novartis as an SAE Establish causality	ALT, AST, TBL, Alb, PT, ALP and γ GT until resolution ^c (frequency at investigator discretion)
> 3 x ULN accompanied by symptoms ^b	Medically significant	Discontinue the study drug immediately Hospitalize if clinically appropriate Report to Novartis as an SAE Establish causality	ALT, AST, TBL, Alb, PT, ALP and γ GT until resolution ^c (frequency at investigator discretion)
> 3 to \leq 5 x ULN (patient is asymptomatic)	AESI	Central laboratory to report to Investigator & Novartis Repeat LFT once or twice in the week If elevation persists, establish causality	Investigator discretion Monitor LFT within 1 to 4 weeks or at next visit
\leq 3 x ULN (patient is asymptomatic)	N/A	Repeat LFT at next visit	
ALP (isolated)			
> 5 x ULN	Medically significant	Repeat LFT within 48 hours If elevation persists, report to Novartis as an SAE Establish causality	Investigator discretion Monitor LFT within 1 to 4 weeks or at next visit
> 2 to \leq 5 x ULN (patient is asymptomatic)	AESI	Central laboratory to report to Investigator & Novartis Repeat LFT once or twice in the week If elevation persists, establish causality	Investigator discretion Monitor LFT within 1 to 4 weeks or at next visit
\leq 2 x ULN (patient is asymptomatic)	N/A	Repeat LFT at next visit	

Criteria	Event type	Actions required	Follow-up monitoring
asymptomatic)			
TBL (isolated)			
> 3 x ULN	Medically significant	Repeat LFT within 48 hours If elevation persists, discontinue the study drug immediately Hospitalize if clinically appropriate Report to Novartis as an SAE Establish causality	ALT, AST, TBL, Alb, PT, ALP and γ GT until resolution ^c (frequency at investigator discretion) Test for hemolysis (e.g., reticulocytes, haptoglobin, unconjugated [indirect] bilirubin)

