> 1.5 to \leq 3 x ULN (patient is asymptomatic)	AESI	Central laboratory to report to Novartis Repeat LFT once or twice in the week. If elevation persists, establish causality	investigator discretion Monitor LFT within 1 to 4 weeks or at next visit
\leq 1.5 x ULN (patient is asymptomatic)	N/A	Repeat LFT at next visit	
Preferred terms			
Jaundice	Medically significant	Discontinue the study drug immediately Hospitalize the patient Report to Novartis as an SAE Establish causality	ALT, AST, TBL, Alb, PT, ALP and γ GT until resolution ^c (frequency at investigator discretion)
"Drug-related hepatic disorders - severe events only" SMQ AE	Medically significant	Discontinue the study drug hospitalization if clinically appropriate Report to Novartis as an SAE Establish causality	Investigator discretion

^a Elevated ALT/AST > 3 x ULN and TBL > 2 x ULN but with no notable increase in ALP to > 2 x ULN

^b General malaise, fatigue, abdominal pain, nausea, or vomiting, rash with eosinophilia

^c Resolution is defined as an outcome of one of the following: return to baseline values, stable values at three subsequent monitoring visits at least 2 weeks apart, remain at elevated level after a maximum of 6 months, liver transplantation, and death.

15 Appendix 3: The PASI Scoring System

Body Region	Erythema (E)	Thickening (plaque elevation, induration, I)	Scaling (desquamation, D)	Area score (based on true area %, A)*
Head (H)†	0=none	0=none	0=none	0 = 0%
	1=slight	1=slight	1=slight	1 = 1-9%
	2=moderate	2=moderate	2=moderate	2 = 10-29%
	3=severe	3=severe	3=severe	3 = 30-49%
	4=very severe	4=very severe	4=very severe	4 = 50-69%
				5 = 70-89%
			6 = 90-100%	
Trunk (T)‡	0=none	0=none	0=none	0 = 0%
	1=slight	1=slight	1=slight	1 = 1-9%
	2=moderate	2=moderate	2=moderate	2 = 10-29%
	3=severe	3=severe	3=severe	3 = 30-49%
	4=very severe	4=very severe	4=very severe	4 = 50-69%
				5 = 70-89%
			6 = 90-100%	
Upper limbs (U)	0=none	0=none	0=none	0 = 0%
	1=slight	1=slight	1=slight	1 = 1-9%
	2=moderate	2=moderate	2=moderate	2 = 10-29%
	3=severe	3=severe	3=severe	3 = 30-49%
	4=very severe	4=very severe	4=very severe	4 = 50-69%
				5 = 70-89%
			6 = 90-100%	
Lower limbs (L)§	0=none	0=none	0=none	0 = 0%
	1=slight	1=slight	1=slight	1 = 1-9%
	2=moderate	2=moderate	2=moderate	2 = 10-29%
	3=severe	3=severe	3=severe	3 = 30-49%
	4=very severe	4=very severe	4=very severe	4 = 50-69%
				5 = 70-89%
			6 = 90-100%	

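### The protocol admits Gilbert patients with bilirubin above 1.5 x ULN, but its liver-event tables treat the same stable value as an AESI, or above 3 x ULN as an SAE with a stop

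*Protocol*

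**What the plan says.** **Entry.** Criterion 16 in Protocol section 4.2 lists among its exclusions "total bilirubin > 1.5 × ULN (except for subjects with Gilbert Syndrome". No maximum is set for Gilbert patients. SAP section 5.5, Table 1 (EXCL16), repeats the exception.

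**Event definitions.** Protocol Appendix 2, Table 14-1, defines the laboratory events of special interest as "ALT or AST > 3 x ULN ALP > 2 x ULN TBL > 1.5 x ULN". In the SAE tier it lists total bilirubin (TBL) above 3 x ULN on its own line. The restriction to conjugated bilirubin belongs to the neighbouring ALT/AST, ALP and Hy's Law entries, not to this one, as the run of the text shows: "mainly conjugated fraction]) TBL > 3 x ULN Potential".

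**Actions.** Table 14-2 heads its column as required actions. It has two isolated-TBL rows that matter here:
- Above 1.5 and up to 3 x ULN, asymptomatic: "Central laboratory to report to Novartis Repeat LFT once or twice in the week. If elevation persists, establish causality". No stop.
- Above 3 x ULN: repeat within 48 hours, stop study drug immediately if the elevation persists, report as an SAE. Follow-up includes "Test for hemolysis (e.g., reticulocytes, haptoglobin, unconjugated [indirect] bilirubin", but that result changes neither the class nor the stop.

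**Baseline.** In the liver appendix, baseline appears only in footnote c, where resolution may be "return to baseline values, stable values at three subsequent monitoring visits at least 2 weeks apart". That settles when an event ends, not whether one has begun.

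**Governing text.** Section 7.3 describes "Medically significant liver events that are considered as serious adverse events and consist of marked elevations of LFTs" and sends any event meeting the Table 14-1 criteria for that tier to SAE reporting. It also says to repeat tests and to stop drug where appropriate.

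**The concern.** The exception in criterion 16 means that a raised bilirubin in Gilbert syndrome is not, by itself, a reason to keep a patient out. The event tables then treat the same unchanged value as a liver signal once the patient is on drug. Gilbert syndrome is named only in criterion 16 and its SAP restatement.

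Between 1.5 and 3 x ULN the consequence is an unnecessary report and repeat liver tests. Above 3 x ULN it is an avoidable SAE report and loss of treatment for a finding that was known at entry. Section 5.5.5 permits no treatment interruption, and section 5.5.9 says withdrawn patients are not replaced.

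**Working it through.** The plan states no figure on this point, so there is none to reproduce. The check sets the thresholds side by side and then tests the proposed remedy.

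**1. Thresholds (multiples of ULN)**

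| Rule | Source | TBL limit | Gilbert or baseline exception |
|---|---|---|---|
| Exclusion | Criterion 16 | > 1.5 | Gilbert exempt, no cap |
| AESI | Tables 14-1, 14-2 | > 1.5 (to 3) | none |
| SAE, stop if persistent | Tables 14-1, 14-2 | > 3 | none |

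The exclusion limit and the AESI limit are equal. Any patient who needs the exception and whose bilirubin stays where it was therefore meets an event row during treatment. This follows from the equality of the two limits and is not a measured rate.

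**2. Stable Gilbert patients walked through the rows**
- 1.8 x ULN: eligible; AESI row; report and repeat tests; no stop.
- 2.4 x ULN: eligible; AESI row; the same actions; no stop.
- 3.2 x ULN: eligible; SAE row. A stable value persists on the 48-hour repeat, so the row calls for a stop.

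Total bilirubin is scheduled at visits 7 to 12 (6) and E1 to E4 (4), so 6 + 4 = 10 samples after Day 1 (section 6.5.4.2). A persisting value is one event, followed until resolved or judged permanent (section 7.1), not ten.

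**3. Number of patients.** The documents give no Gilbert frequency or bilirubin distribution. Purely as an assumption, 0 to 3% of 406 enrolled is 0 to 0.03 x 406 = 12.18, that is 0 to 12 patients. The number above 3 x ULN is unknown and may be zero.

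**4. What margin would a baseline-relative rule need?** Model: log-normal values around a constant level, 2 pre-dose samples (visits 2 and 3), 10 later samples, each with an independent repeat; 300,000 simulated patients. The within-patient CVs of 10, 20 and 30% are assumptions.

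*No margin.* The rule fires on any later value above the higher pre-dose value. For 12 exchangeable values, the chance that the largest is among the 10 later ones is 10/12 = 83%, at any CV. That is unusable.

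*Margin of 1.5 x the pre-dose mean:*

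| | CV 10% | CV 20% | CV 30% |
|---|---|---|---|
| False trigger over 10 samples, single value | 0.4% | 27% | 53% |
| False trigger over 10 samples, confirmed on repeat | 0.0% | 5% | 18% |
| Confirmed at one visit: sustained 1.5-fold rise | 30% | 29% | 28% |
| Confirmed at one visit: sustained doubling | 98% | 78% | 63% |
| Confirmed at one visit: sustained tripling | 100% | 99% | 94% |

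The false-trigger figures are upper bounds, because the row's absolute ULN limit must be met as well. Confirmation is what makes the rule workable. The cost is weak detection of modest rises. A 1.5-fold rise from 2.4 reaches 2.4 x 1.5 = 3.6 x ULN, above the present SAE limit, yet would be confirmed at a given visit less than a third of the time. A patient stable at 3.2 x ULN would have to exceed 3.2 x 1.5 = 4.8 x ULN, unless the bilirubin is mainly conjugated.

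**The case against.** The best defence is that the tables do not stand alone. Section 7.1 makes an abnormal laboratory value an adverse event only if it causes symptoms, is clinically significant or needs therapy. It judges significance partly by change from baseline and by what is typical for the underlying disease. An SAE is an event that appears or worsens. Section 7.3 allows stopping where appropriate. On this reading a known, stable Gilbert value is no event at all. This stands in part: an investigator has room to act sensibly, and a mandatory stop is not beyond argument. It does not remove the conflict, because section 7.3 also routes every event meeting the Table 14-1 criteria to SAE reporting, and Table 14-2 presents its actions as required.

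A second defence is that the missing conjugated-fraction qualifier may be deliberate: the haemolysis work-up suggests that the row above 3 x ULN is meant to catch unconjugated rises. That is fair. It is a reason to keep the row for a true rise, not to apply it to an unchanged value.

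Two stronger readings are tempting.
- Because adverse events count from consent, a reader might infer that the qualifying visit 2 sample is itself a reportable liver event. The documents do not support this. Section 7.3 is directed at the hepatotoxicity of the drug, and a pre-existing value is neither new nor worsened at screening.
- A reader might also infer that the notable-bilirubin counts in SAP section 2.8.3 (above 2 x ULN) are distorted. Those counts are descriptive, and the shift tables beside them already condition on baseline. No SAP change is needed.

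**Conclusion.** The mismatch is real and rests on the text alone. Patients deliberately admitted above 1.5 x ULN meet an AESI row, or above 3 x ULN an SAE row with discontinuation, at an unchanged value. The severity is minor, and the remedy is a cheap improvement.

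A reader might infer that the trial's safety or efficacy results are at risk; the documents do not show that. A stable pre-existing value is not treatment-emergent under SAP section 2.8.1. The SAP's events of special interest are neutropenia and candida infection, and its risk-plan table contains no bilirubin event. PASI 90 and the sample size are not shown to be affected. What remains is unnecessary reporting and repeat testing in a few patients, and an avoidable SAE report and stop in any patient stably above 3 x ULN. The range of 0 to 12 patients rests on an assumed frequency, and the operating figures for the remedy rest on assumed CVs.

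**What to change.** Add one footnote to the isolated-TBL rows of Tables 14-1 and 14-2, to this effect:

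> In patients with Gilbert syndrome documented at screening, from first dose these rows apply only if bilirubin is mainly conjugated, or if TBL has risen from the pre-dose (visit 2/3) level by a sponsor-set margin, confirmed on the repeat LFT already required. A stable pre-dose value is recorded as medical history.

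The sponsor should choose the margin with the table above in view and say what counts as documentation of Gilbert syndrome. Conditioning on a repeat has a precedent in the isolated ALP row above 5 x ULN: "If elevation persists, report to Novartis as an SAE Establish causality". Leave the Hy's Law, ALT/AST, ALP and jaundice rows unchanged.

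Cost: a written amendment under section 11.1, which can travel with the next one, and a bilirubin fraction on an existing or repeat sample in a few patients, since the scheduled panel lists total bilirubin only. The clinical downside is a less sensitive isolated-bilirubin alert in known Gilbert patients, most of all for modest unconjugated rises.

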4.3 Eligibility criteria for entering the extension treatment period

1. Patients who have completed the CAIN457AIT01 core study.
2. Written informed consent for protocol amendment 2 must be obtained before patients proceed to the extension treatment period.
3. Patients must be deemed to be benefiting from the study drug based on at least a PASI 75 response rate after 24 weeks of treatment.

5 Treatment

5.1 Protocol requested treatment

5.1.1 Investigational treatment

Secukinumab 300 mg (two s.c. injections of secukinumab 150 mg).

Secukinumab will be administered as solution for injection in a pre-filled syringe: clear to opalescent, colorless to slightly yellowish liquid (150 mg/1.0 mL) in a 1 mL long, single-use, prefilled glass syringe with fluortec-coated bromobutyl rubber plunger stopper staked 27G ½ inch needle and rigid needle sheet and needle safety device. The pre-filled syringe is incorporated into a triangular auto-injector/pen.

The study treatment will be administered by the site staff during the visit. Patients enrolled in the extension period will self-administer secukinumab and will be asked to keep a self-administration log during this period.

5.1.2 Additional study treatment

No additional treatment beyond investigational treatment is requested for this trial.

5.2 Treatment arms

Not applicable, all patients will receive secukinumab 300 mg.

5.3 Treatment assignment

All patients will receive secukinumab 300 mg subcutaneously.

5.4 Treatment blinding

Not applicable, this is an open label study. All patients will receive secukinumab 300 mg.

5.5 Treating the patient

5.5.1 Patient numbering

Each patient is uniquely identified by a Subject Number which is composed of the site number assigned by Novartis and a sequential number assigned by the investigator. Once assigned to a patient, the Subject Number will not be reused.

Upon signing the informed consent form, the patient is assigned the next sequential number as given by the investigator using the next blank Case Report Form (CRF) book available from the Electronic Data Capture (EDC) system.

If an enrolled patient fails to be treated for any reason, the reason will be entered on the Screening Study Disposition CRF.

5.5.2 Dispensing the investigational treatment

Each study site will be supplied by Novartis with investigational treatment in packaging of identical appearance. This is an open label study.

5.5.3 Handling of study treatment

5.5.3.1 Handling of investigational treatment

Investigational treatment must be received by a designated person at the study site, handled and stored safely and properly, and kept in a secured location to which only the investigator and designees have access. Upon receipt, all investigational treatment should be stored according to the instructions specified on the labels. Clinical supplies are to be dispensed only in accordance with the protocol.

Medication labels will be in the local language and comply with the legal requirements of each country.

The investigator must maintain an accurate record of the shipment and dispensing of investigational treatment in a drug accountability log. Monitoring of drug accountability will be performed by the field monitor during site visits and at the completion of the trial.

At the conclusion of the study, and as appropriate during the course of the study, the investigator will return all unused investigational treatment, packaging, drug labels, and a copy of the completed drug accountability log to the Novartis monitor or to the Novartis address provided in the investigator folder at each site.

Handling of other study treatment: not applicable.

